#### Has been changed to read:

The treatment duration will be 12 weeks for all subjects except HCV GT1a-infected subjects with compensated cirrhosis who will receive treatment for 24 weeks. Treatment duration of 12 weeks for HCV GT1a-infected subjects with compensated cirrhosis may be selected by the investigator where consistent with the approved local label.

**Table 5. Treatment Regimen and Duration**

#### Previously read:

Subjects		Treatment Regimen	Treatment Duration
HCV GT1a-infected subjects*	without cirrhosis	ABT-450/r/ABT-267 + ABT-333 + RBV	12 weeks
	with compensated cirrhosis who are: 
 
• treatment-naïve
 
• prior IFN/RBV or pegIFN/RBV partial responder
 
• prior IFN/RBV or pegIFN/RBV relapser
 
• prior IFN/RBV or pegIFN/RBV relapse/breakthrough
 
• interferon intolerant
 
• interferon experienced-other
 
		
	with compensated cirrhosis who are: 
 
• prior IFN/RBV or pegIFN/RBV null responders
 
• prior IFN/RBV or pegIFN/RBV nonresponder
 
	ABT-450/r/ABT-267 + ABT-333 + RBV	24 weeks
HCV GT1b-infected subjects	without cirrhosis	ABT-450/r/ABT-267 + ABT-333	12 weeks
	with compensated cirrhosis	ABT-450/r/ABT-267 + ABT-333 + RBV	12 weeks

\* Includes subjects that are unable to be subtyped or with mixed subtypes.

**Has been changed to read:**

Subject Population	Treatment Regimen*	Treatment Duration
Genotype 1a, without cirrhosis	ABT-450/r/ABT-267 + ABT-333 + ribavirin	12 weeks
Genotype 1a, with cirrhosis	ABT-450/r/ABT-267 + ABT-333 + ribavirin	24 weeks**
Genotype 1b, without cirrhosis	ABT-450/r/ABT-267 + ABT-333	12 weeks
Genotype 1b, with cirrhosis	ABT-450/r/ABT-267 + ABT-333 + ribavirin	12 weeks

\* Follow the genotype 1a dosing recommendations in patients with an unknown genotype 1 subtype or with mixed genotype 1 infection.

\*\* Treatment for 12 weeks may be considered in some patients where consistent with the approved local label.

**Section 5.2.1 Inclusion Criteria**

**Criterion 2**

**Fourth bullet, second sub-bullet, second sentence previously read:**

(Note: Estrogen-containing hormonal contraceptives, including oral, injectable, implantable, patch and ring varieties, may not be used during study drug treatment).

**Has been changed to read:**

(Note: Ethinyl estradiol-containing hormonal contraceptives, including oral, injectable, implantable, patch and ring varieties, may not be used during study drug treatment).

**Table 6. Medications Contraindicated for Use with the Study Drug Regimen Previously read:**

Alfuzosin	Estrogen-containing Medications for Systemic Use	Phenytoin
Astemizole	Fusidic Acid	Pimozide
Carbamazepine	Gemfibrozil	Rifampin
Dihydroergotamine	Lovastatin	Sildenafil*
Efavirenz	Methylergonovine	Simvastatin
Ergotamine	Midazolam (oral)	St. John's Wort
Ergonovine	Phenobarbital	Terfenadine
		Triazolam

\* When used for the treatment of pulmonary arterial hypertension.

Not all medications contraindicated with ritonavir and ribavirin are listed above. Refer to the most current package inserts or product labeling of ritonavir and ribavirin for a complete list of contraindicated medications.

**Has been changed to read:**

For medications contraindicated with AbbVie's 3 DAA regimen, refer to the recommended prescribing information section of the approved local product labels in countries where the regimen contained in this study (i.e., ABT-450/r/ABT-267 and ABT-333) has received marketing authorization. If locally approved labels are not available, refer to the following Contraindicated Medication list:

Alfuzosin	Ethinyl estradiol-containing medications	Pimozide
Astemizole	Fusidic Acid	Rifampin
Carbamazepine	Gemfibrozil	Salmeterol
Cisparide	Lovastatin	Sildenafil*
Dihydroergotamine	Methylergonovine	Simvastatin
Efavirenz	Midazolam (oral)	St. John's Wort
Ergotamine	Phenobarbital	Terfenadine
Ergonovine	Phenytoin	Triazolam

\* When used for the treatment of pulmonary arterial hypertension.

Note: Not all medications contraindicated with ritonavir, ribavirin, and 3DAA regimen are listed above. Refer to the most current package inserts or product labeling of ritonavir and ribavirin for a complete list of contraindicated medications.

## **Section 5.2.2 Exclusion Criteria**

### **Criterion 4 previously read:**

Use of known strong inducers of cytochrome P450 3A (CYP3A) or strong inducers of cytochrome P450 2C8 (CYP2C8) or strong inhibitors of CYP2C8 within 2 weeks of the respective medication/supplement, prior to initial dose of study drug.

### **Has been changed to read:**

Use of known moderate or strong inducers of cytochrome P450 3A (CYP3A) or strong inducers of cytochrome P450 2C8 (CYP2C8) or strong inhibitors of CYP2C8 within 2 weeks of the respective medication/supplement, prior to initial dose of study drug.

## **Section 5.2.2 Exclusion Criteria**

### **Criterion 6 previously read:**

Current enrollment in another interventional clinical study, previous enrollment in this study, prior or current use of any investigational or commercially available anti-HCV agents other than IFN or RBV (including previous exposure to ABT-450, ABT-267 or ABT-333), or receipt of any investigational product within 6 weeks prior to study drug administration.

### **Has been changed to read:**

Current enrollment in another interventional clinical study, previous enrollment in this study, prior or current use of any investigational or commercially available anti-HCV agents other than IFNs or RBV (including previous exposure to ABT-450, ABT-267 or ABT-333), or receipt of any investigational product within 6 weeks prior to study drug administration.

### **Section 5.2.3.2 Concomitant Therapy**

#### **Second paragraph, third sentence previously read:**

The investigator or qualified designee should review the concomitant medication(s) labels and utilize the drug-drug interactions (DDI) tool that will be provided by the sponsor to screen concomitant medications at each visit for potential DDIs with study drugs.

#### **Has been changed to read:**

The investigator or qualified designee should review the locally approved labels for concomitant medication(s), ribavirin and ritonavir and, where available, ABT-450, ABT-267, and ABT-333 and utilize the drug-drug interactions (DDI) tool that will be provided by the sponsor to screen concomitant medications at each visit for potential DDIs with study drugs.

### **Section 5.2.3.2 Concomitant Therapy**

#### **Fifth paragraph previously read:**

Prior to enrollment, subjects should agree to practice two effective methods of birth control while receiving study drugs starting with Study Day 1 for 30 days after stopping study drug or for 7 months after stopping study drug if receiving RBV. Subjects using systemic estrogen-containing medications (including estrogen-containing oral contraceptives) have a higher risk for elevated ALT levels. Subjects using these medications must discontinue them at least 2 weeks prior to study drug administration or 10 half-lives (if known), whichever is longer. Subjects may replace the systemic estrogen-containing contraceptive with a progestin-only hormonal contraceptive method.

#### **Has been changed to read:**

Prior to enrollment, subjects should agree to practice two effective methods of birth control while receiving study drugs starting with Study Day 1 for 30 days after stopping study drug or for 7 months after stopping study drug if receiving RBV. Subjects using ethinyl estradiol-containing medications (including combination oral contraceptives) have a higher risk for elevated ALT levels. Subjects using these medications must discontinue

them at least 2 weeks prior to study drug administration or 10 half-lives (if known), whichever is longer. Subjects may replace the ethinyl estradiol-containing contraceptive with a progestin-only hormonal contraceptive method.

### Section 5.2.3.3 Prohibited Therapy

#### First paragraph previously read:

In addition to the medications listed above in Table 6, use of known strong inducers of CYP3A or strong inhibitors or inducers of CYP2C8 is prohibited within 2 weeks or 10 half-lives of the medication, whichever is longer, prior to the initial dose of study drugs and through the first 2 weeks after the subject has completed study drugs in the Treatment Period.

#### Has been changed to read:

In addition to the medications listed above in Table 6, use of known moderate or strong inducers of CYP3A or strong inhibitors or inducers of CYP2C8 is prohibited within 2 weeks or 10 half-lives of the medication, whichever is longer, prior to the initial dose of study drugs and through the first 2 weeks after the subject has completed study drugs in the Treatment Period.

### Table 7. Study Activities

Delete: row "Study Drug Returned for IRT Reconciliation"

Activity	Treatment Period (TP)						Post-Treatment (PT) Period
	Screening	Day 1 a	Week 2	Week 4	Week 12 b	End of Treatment (EOT) (Week 12 or 24) or Treatment D/C b,c	PT Weeks 4 d , 12, 24, 52, 104, 156, 208, 260 or PT D/C c
Study Drug Returned for IRT Reconciliation			X	X	X	X b	

**Table 7. Study Activities**

**Table note "j."**

**Add new last sentence to second paragraph**

Females of childbearing potential that were treated with DAAs only in the Treatment Period should have urine pregnancy testing done through Post-Treatment Week 4.

**Section 5.3.1.1 Study Procedures**

**Subsection Pregnancy Test**

**Add: new third bullet**

Females of childbearing potential that were treated with DAAs only in the Treatment Period should have urine pregnancy testing done through Post-Treatment Week 4.

**Table 8. Clinical Laboratory Tests**

**"Clinical Chemistry" column**

**Add:**

Alpha-Fetoprotein (AFP)b

**Section 5.3.1.1 Study Procedures**

**Subsection Concomitant Medication Assessment**

**First paragraph, second sentence previously read:**

[figure not shown]
The investigator or qualified designee should review concomitant medication(s) label(s) and should also utilize the DDI tool that will be provided by the sponsor for potential drug interactions.

**Has been changed to read:**

The investigator or qualified designee should review the locally approved labels for concomitant medication(s), ribavirin and ritonavir and, where applicable, ABT-450, ABT-267, and ABT-333 and should also utilize the DDI tool that will be provided by the sponsor for potential drug interactions.

**[contact]**

**Table 12. Ribavirin Dose Modification Guidelines in Management of Hemoglobin Decreases**

**Table note previously read:**

- \* 1st dose reduction of RBV is by 200 mg/day. If needed, 2nd dose reduction of RBV is by an additional 200 mg/day. Subjects whose dose of RBV is reduced to 600 mg daily receive one 200 mg tablet in the morning and two 200 mg tablets in the evening

**Has been changed to read:**

- \* 1st dose reduction of RBV is by 200 mg/day or per local label. If needed, 2nd dose reduction of RBV is by an additional 200 mg/day. Subjects whose dose of RBV is reduced to 600 mg daily receive one 200 mg tablet in the morning and two 200 mg tablets in the evening.

**Section 9.1 Independent Ethics Committee (IEC) or Institutional Review Board (IRB)**

**Second paragraph, first sentence previously read:**

Any amendments to the protocol will require IEC/IRB approval prior to implementation of any changes made to the study design.

[figure not shown]
**Has been changed to read:**

Any amendments to the protocol will require IEC/IRB approval, and approved by Regulatory Authority (ies), if required by local regulations, prior to implementation of any changes made to the study design.

3.0 Introduction

This statistical analysis plan (SAP) describes the statistical analyses to be completed by AbbVie Statistics and Statistical Programming for Study Protocol M14-423. TOPAZ-I (Study M14-423) and companion study TOPAZ-II (Study M14-222) are designed together and share the primary objective of assessing the effect of treatment response (assessed by SVR₁₂ status, i.e., HCV ribonucleic acid (RNA) < lower limit of quantification (LLOQ) 12 weeks following treatment) on long-term clinical outcomes in adults with genotype 1 (GT1) chronic hepatitis C virus (HCV) infection who received treatment with ABT-450/r/ABT-267 and ABT-333 with or without ribavirin, as measured by all-cause death, liver-related death, liver decompensation, liver transplantation, and hepatocellular carcinoma.

In the TOPAZ-I and TOPAZ-II studies, the primary objective is to assess the effect of treatment response on long-term clinical outcomes, based on the data from both studies combined. The studies differ based on geographic region (this study will be conducted outside the US while the TOPAZ-II study will be conducted in the US) and based on certain procedures that are not related to the primary outcome. For example, this study will assess the long-term change from baseline in liver elastography, and the TOPAZ-II study will utilize a Subject Care Plan Model to facilitate subjects' adherence to the study drug.

The SAP provides details to guide the analyses for baseline, efficacy, and safety variables and describes the populations and variables that will be analyzed and the statistical methods that will be utilized. An interim analysis (after all subjects reach Post-Treatment [PT] Week 12 or prematurely discontinue the study) and an end of study analysis will be conducted for Study M14-423. Analyses will be performed using SAS[®] Version 9.3 (SAS Institute, Inc., Cary, NC) or later under the UNIX operating system.

4.0 Study Objectives, Design and Procedures

4.1 Objectives

The primary objective of this study is to evaluate the effect of virologic response to treatment (assessed by SVR₁₂ status) on the long-term progression of liver disease in adults with chronic HCV GT1 infection who receive treatment with ABT-450/r/ABT-267 and ABT-333 with or without ribavirin, as measured by all-cause death, liver-related death, liver decompensation, liver transplantation, and hepatocellular carcinoma.

The secondary objectives are to evaluate the long-term progression of fibrosis and sustained virologic response in adults with GT1 chronic HCV infection who received treatment with ABT-450/r/ABT-267 and ABT-333 with or without ribavirin. Progression of fibrosis is measured by change from baseline in liver stiffness using transient elastography (FibroScan[®]), when available. Sustained virologic response is evaluated by the percentage of subjects achieving SVR₁₂.

4.2 Design Diagram

[figure not shown]
Study M14-423 is a Phase 3b, open-label, multi-center study, which is designed together with companion Study M14-222 (TOPAZ-II) to share the primary objective of assessing the effect of treatment response on long-term clinical outcomes in adults with GT1 chronic HCV infection with or without compensated cirrhosis, who are either treatment-naïve or IFN/RBV (IFN or peg IFN/RBV) treatment-experienced.

Approximately 1650 subjects will be enrolled in Study M14-423 at approximately 200 sites outside the US. The number of cirrhotic subjects (fibrosis stage of F4) will be limited to approximately 400 subjects; the number of subjects enrolled without fibrosis or with portal fibrosis without septa (fibrosis stage of F0 or F1) will be limited to approximately 1000 subjects.

As shown in [Figure 1](#), subjects meeting eligibility criteria will be enrolled to either 12 or 24 weeks of treatment according to HCV subgenotype and presence of cirrhosis. Subjects

who receive at least one dose of study drug will be followed in the Post-Treatment Period for up to 5 years (PT Week 260).

Figure 1. Study Schematic

The duration of the study will be 272 weeks (for subjects receiving a 12-week treatment) or 284 weeks (for subjects receiving a 24-week treatment), not including a screening period of up to 42 days, consisting of a 12-week or 24-week Treatment Period and a 260-week Post-Treatment (PT) Period for all subjects who receive at least one dose of study drug.

Treatment Period

Subjects who meet the eligibility criteria will be enrolled to either 12 or 24 weeks of combination therapy with or without RBV as described below and in [Table 1](#).

All HCV GT1-infected subjects who are either treatment-naïve or treatment-experienced will receive ABT-450/r/ABT-267 150/100/25 mg once daily (QD) and ABT-333 250 mg twice daily (BID). Subjects with HCV GT1a infection and all GT1-infected subjects with compensated cirrhosis will also receive RBV with weight-based dosing 1000 or 1200 mg BID.

The treatment duration will be 12 weeks for all subjects except HCV GT1a-infected subjects with compensated cirrhosis, who will receive treatment for 24 weeks, unless a treatment duration of 12 weeks is selected by the investigator based on the subject's prior

treatment history. Subjects will receive a study drug regimen according to criteria listed in Table 1. Upon completing the Treatment Period or premature discontinuation of the Treatment Period, subjects will enter the Post Treatment (PT) Period.

Table 1. Treatment Regimen and Duration

Subject Population	Treatment Regimen*	Treatment Duration
Genotype 1a, without cirrhosis	ABT-450/r/ABT-267 + ABT-333 + ribavirin	12 weeks
Genotype 1a, with cirrhosis	ABT-450/r/ABT-267 + ABT-333 + ribavirin	24 weeks**
Genotype 1b, without cirrhosis	ABT-450/r/ABT-267 + ABT-333	12 weeks
Genotype 1b, with cirrhosis	ABT-450/r/ABT-267 + ABT-333 + ribavirin	12 weeks

* Note: Follow the genotype 1a dosing recommendations in patients with an unknown genotype 1 subtype or with mixed genotype 1 infection.

** Treatment for 12 weeks may be considered in some patients where consistent with the approved local label.

Post-Treatment Period

Subjects who receive at least one dose of study drug in the Treatment Period and either complete treatment or prematurely discontinue study drug will be followed in the Post-Treatment Period for up to 260 weeks. At the Post-Treatment visits, subjects will be assessed for antiviral response, progression of liver fibrosis, patient reported outcomes (PROs) and clinical outcomes, including all-cause death, liver-related death, and occurrence of hepatocellular carcinoma, liver decompensation and liver transplantation.

The Post-Treatment Period will begin the day following the last dose of study drug treatment.

4.3 Sample Size

Assuming 4% of subjects do not achieve SVR₁₂ and assuming the 5-year event rate of the composite clinical outcome is 20% in the non-SVR₁₂ subjects, with a 75% reduction in SVR₁₂ subjects (Hazard Ratio of 0.25),^{1,2} then based on two-sample log rank test (using EAST 6.0), a sample size of at least 2000 subjects enrolled in TOPAZ-I (planned to enroll 1650 subjects) and TOPAZ II (planned to enroll 600 subjects) provides greater than 80%

power to reject the null hypothesis of no difference between SVR₁₂ and non-SVR₁₂ subjects in the rate of clinical outcome events. Power calculations were based on a dropout rate of up to 20% for the hazard ratio.

4.4 Planned Analysis

The primary analysis to evaluate the effect of response to treatment on clinical outcomes, will occur at the final analysis after all subjects have completed the study or prematurely discontinued the study. An interim analysis to assess the percentage of subjects achieving SVR₁₂ will occur after all subjects have completed the Post-Treatment Week 12 Visit or prematurely discontinued the study. For both final and interim analyses, data will be locked after performing appropriate data cleaning. Data after the interim analysis will be added to a subsequent version of the database. SAS[®] (SAS Institute, Inc., Cary, NC) for the UNIX operating system will be used for all analyses. All statistical tests and all confidence intervals will be two-sided with an α level of 0.05.

All analyses will be conducted by statisticians and statistical programmers at AbbVie or the designee according to the methodologies specified in this SAP.

There is no intention of shortening the follow-up time of subjects based on efficacy findings from the interim analysis. The intention is to follow all subjects who receive study drug for 260 weeks following treatment. There will be no statistical adjustment employed due to this interim analysis.

5.0 Analysis Populations

5.1 Definition for Analysis Populations

5.1.1 Intention-to-Treat (ITT) Population

The Intention-to-treat (ITT) population will consist of all enrolled subjects in this study (ITT-I) and the companion study TOPAZ-II (ITT-II) who receive at least one dose of study drug.

The primary efficacy analysis on clinical outcomes will be performed on the ITT population.

5.1.2 Intention-to-Treat-I (ITT-I) Population

The ITT-I population will consist of all enrolled subjects in this study who receive at least one dose of study drug. The data from the ITT-I population will be presented for all subjects regardless of treatment duration and ribavirin use in one column.

All efficacy, patient reported outcomes and resistance analyses, except for the primary efficacy analysis, will be performed on the ITT-I population. In addition, sensitivity analyses of SVR₁₂ will be performed on the Modified Intention-to-Treat-I Genotype (mITT-I-GT) population and Modified Intention-to-Treat-I Genotype and Virologic Failure (mITT-I-GT+VF) population, respectively, as specified in Section 10.6.

5.1.3 Safety Population

All subjects in this study who receive at least one dose of study drug will be included in the safety population. Safety analyses will be performed on the safety population and be presented also for all subjects together. In other words, the safety population will be the same as the ITT-I population.

Demographic and safety analyses will be performed on the safety population.

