Transient elevations in total (predominantly indirect) bilirubin may occur due to ABT-450 inhibition of the bilirubin transporters OATP1B1 and OATP1B3, and RBV-induced hemolysis. The elevations generally peaked by Weeks 1 – 2, declined through the end of

---

treatment and returned to within the normal range by 4 weeks post-treatment. Rates of hyperbilirubinemia were lower in subjects treated with 3-DAA without RBV compared to 3-DAA with RBV. The rates and degree of hyperbilirubinemia were higher in patients with cirrhosis, but the temporal pattern of elevation followed by resolution was similar and few were symptomatic (jaundice). Rates of  $\geq$  Grade 2 hemoglobin reductions were 6% among subjects without cirrhosis who received the 3-DAA + RBV regimen for 12 weeks, and 7% and 11% among subjects with cirrhosis who received the 3-DAA + RBV regimen for 12 and 24 weeks, respectively. Grade 3 hemoglobin values were rare. The decline in hemoglobin was largely managed with RBV dose reductions; use of hematologic growth factors and blood transfusion were rare. The anemia reported in the clinical trials was primarily observed when the 3-DAA regimen was administered with RBV.

Transient asymptomatic postbaseline serum ALT elevations of  $> 5 \times$  ULN occurred at a frequency of 1% across active treatment arms and were evaluated by an external hepatic panel. The ALT elevations were asymptomatic, usually occurred within the first 4 weeks of treatment and typically declined with ongoing treatment. A disproportionate number of the cases were in women on concurrent systemic ethinyl estradiol-containing therapy (i.e., combination contraceptives) and discontinuation of the hormonal therapy with continuation or brief interruption of the DAA regimen led to resolution in serum ALT elevation. Concomitant use of systemic ethinyl estradiol-containing medications is a risk factor for these postbaseline elevations in serum ALT. There was no increase in the risk of ALT elevations greater than  $5 \times$  ULN in subjects on estrogens other than ethinyl estradiol (i.e., estradiol, conjugated estrogens) or in subjects on only progestins. Among the cases of serum ALT elevation thought to be related to the DAA regimen, none resulted in hepatic dysfunction and they generally resolved or improved with ongoing treatment. All cases had resolved completely in the post-treatment follow-up.

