HCV RNA < LLOQ Analyses for SVR

If a subject is missing an HCV RNA value for the visit window associated with the analysis of SVR after performing the imputations described above, then this value will be imputed with an HCV RNA value from a local laboratory if present; otherwise, the HCV RNA value for this visit will be missing. Subjects with missing HCV RNA data in the analysis window, after imputations, will be imputed as a failure.

HCV RNA Analyses for Relapse and Virologic Failure

If HCV RNA values from the central laboratory are missing but a local laboratory value is present in the appropriate time period, then the local laboratory value will be used to assess post-treatment relapse and on-treatment virologic failure.

Finally, missing sequence data will be imputed as follows in the analysis of the persistence of resistance from the sequences from PT Week 52 through PT Week 260 (5 years). If a signature variant is not detectable by population, clonal or deep sequencing at PT Week 24 (or later), the variant is imputed as not detectable at the PT Week 52 (or timepoints after the sequence with the variant not detectable) and time points thereafter if a sample from Post-Treatment Week 52 or later is not sequenced. If a signature variant is detectable by population, clonal, or deep sequencing at Post-Treatment Week 52 or later, then the variant is imputed as being detectable at earlier time points if the sample at the earlier time point is not sequenced.

7.0 Demographics, Baseline Characteristics, Medical History, and Previous/Concomitant Medications

Demographics, baseline characteristics, medical history, and previous/concomitant medications will be summarized overall and by presence of cirrhosis and genotype 1 subtype on the safety population.

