8.0 Patient Disposition

The number of subjects for each of the following categories will be summarized overall and by each investigator on the safety population.

- Subjects who took at least one dose of study drug;
- Subjects who completed study drug;
- Subjects who discontinued from study drug;
- Subjects who completed the study;
- Subjects ongoing in the Post-Treatment Period at the time of the interim analysis;
- Subjects who discontinued from the study.

The number and percentage of subjects who discontinued study drug will be summarized by reason (all reasons) and by primary reason (per eCRF). Similar summaries will be provided for discontinuations from the study.

The number and percentage of subjects will be summarized for:

- Subjects with interruptions of all study drugs for toxicity management;
- Subjects with any RBV dose modification;
 - Subjects with RBV dose modification due to decrease in hemoglobin;
 - Subjects with RBV dose modification due to decrease in creatinine clearance;
 - Subjects with RBV dose modification due to weight change;
 - Subjects with RBV dose modification due to other reasons;
- Subjects with any RBV dose modification to 0 mg (i.e., RBV interruptions).

Reasons for study drug interruptions and RBV dose modifications will be presented in the CSR listings.

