11.2.1.1 Tabulations of Treatment-Emergent Adverse Events

Adverse event data will be summarized and presented using primary MedDRA system organ classes (SOCs) and preferred terms (PTs) according to the version of the MedDRA coding dictionary used for the study at the time of database lock. The actual version of the MedDRA coding dictionary used will be noted in the clinical study report. The system organ classes will be presented in alphabetical order and the preferred terms will be presented in alphabetical order within each system organ class.

Adverse Event Overview

An overview of adverse events will be presented consisting of the number and percentage of subjects experiencing at least one event for the following adverse event categories:

- Any treatment-emergent adverse event;

- Treatment-emergent adverse events with a "reasonable possibility" of being related to DAAs;
- Treatment-emergent adverse events with a "reasonable possibility" of being related to RBV;
- Severe treatment-emergent adverse events;
- Serious treatment-emergent adverse events;
- Treatment-emergent adverse events leading to discontinuation of study drug;
- Treatment-emergent adverse events leading to interruption of study drug;
- Treatment-emergent adverse events leading to RBV dose modifications;
- Treatment-emergent adverse events leading to death;
- Deaths.

Adverse Event by SOC and PT

The following summaries of adverse events will be generated:

- Treatment-emergent adverse events;
- Treatment-emergent adverse events with a "reasonable possibility" of being related to DAAs;
- Treatment-emergent adverse events with a "reasonable possibility" of being related to RBV;
- Serious treatment-emergent adverse events;
- Moderate or severe treatment-emergent adverse events;
- Severe treatment-emergent adverse events;
- Grade 3 or 4 (see definition below) treatment-emergent adverse events;
- Treatment-emergent adverse events leading to discontinuation of study drug;
- Treatment-emergent adverse events leading to interruption of study drug;
- Treatment-emergent adverse events leading to RBV dose modifications;
- Treatment-emergent adverse events leading to death;
- Treatment-emergent adverse events leading to concomitant medication use (events with other action taken of "concomitant medication prescribed").

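### Safety results are pooled over regimens with and without ribavirin, and ribavirin-specific rows have no ribavirin-recipient denominator, so their percentages do not give the risk of taking ribavirin

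*SAP*

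**What the plan says.** SAP 5.1.3 defines the population broadly: "All subjects in this study who receive at least one dose of study drug will be included in the safety population". It then says "Safety analyses will be performed on the safety population and be presented also for all subjects together", and equates the safety population with ITT-I. For ITT-I, SAP 5.1.2 asks that data be "presented for all subjects regardless of treatment duration and ribavirin use in one column".

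Protocol Table 5 and SAP Table 1 give RBV to all GT1a subjects and to all subjects with cirrhosis. GT1b subjects without cirrhosis receive the three DAAs alone.

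Two sets of rows apply only to RBV recipients:
- SAP 11.2.1.1 tabulates numbers and percentages of adverse events related to RBV, and "Treatment-emergent adverse events leading to RBV dose modifications".
- SAP 8.0 tabulates "Subjects with any RBV dose modification" by reason, and RBV interruptions.

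No RBV-recipient denominator is named for either set. SAP 11.3.2 adds hemoglobin and liver-test grade tables, also without a split.

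Elsewhere the SAP does use the relevant groupings. Under SAP 7.0, demographics, baseline characteristics, medical history and medications "will be summarized overall and by presence of cirrhosis and genotype 1 subtype on the safety population". SAP 10.5 splits SVR12 by cirrhosis and subtype, and by 12 or 24 weeks for GT1 non-b subjects with cirrhosis.

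**The concern.** The protocol treats RBV as the source of much of the regimen's toxicity. Its integrated safety summary says: "The anemia reported in the clinical trials was primarily observed when the 3-DAA regimen was administered with RBV". Protocol Tables 2 and 3 keep regimens with and without RBV, and cirrhotics at 12 and 24 weeks, in separate columns. This study's tables would merge those columns.

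A subject who never receives RBV cannot have an RBV dose modification or an RBV-attributed event. Counting such subjects in the denominator makes the percentage depend on the genotype mix enrolled. A reader who wants the frequency of anemia or RBV dose modification among patients given RBV would read too low a figure. A reader interested in patients with cirrhosis could not find their hemoglobin, bilirubin or general adverse-event rates.

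**Working it through.** **Inputs.** Planned N is 1650 and cirrhotics are capped at about 400 (SAP 4.2). Rates come from Protocol Table 3:

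| Group | Hb < 10 g/dL | Bilirubin > 3 × ULN |
|---|---|---|
| RBV, placebo-controlled, n = 765 | 5.5% | 2.6% |
| RBV, regimen-controlled, n = 401 | 6.2% | 5.7% |
| No RBV, n = 509 | 0% | 0.4% |
| Cirrhotic, RBV 12 weeks, n = 208 | 7.2% | 13.5% |
| Cirrhotic, RBV 24 weeks, n = 172 | 11.0% | 5.2% |

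**Step 1: reproduce the protocol's figure.** The integrated safety summary gives 6% for Grade 2 or worse hemoglobin reductions in non-cirrhotics on RBV for 12 weeks. From Table 3, (765 × 5.5% + 401 × 6.2%) / 1166 = 66.9 / 1166 = 5.74%. If the row below 8.0 g/dL is a separate category, (765 × 5.6% + 401 × 6.7%) / 1166 = 5.98%. Both round to 6%.

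**Step 2: pool the same data as SAP 5.1.3 would.** Adding the 509 RBV-free subjects gives 66.9 / 1675 = 4.0%.

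**Step 3: general relation.** With f the share of subjects receiving RBV, pooled rate = f × (rate with RBV) + (1 − f) × (rate without RBV). For an RBV-specific row the last term is zero, so the relative shortfall is 1 − f.

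**Step 4: this trial.** The GT1b share s is not in the documents. I assume 400 cirrhotics, 1250 non-cirrhotics, the same s in both, GT1b cirrhotics treated for 12 weeks and all other cirrhotics for 24. The number without RBV is 1250 × s. Hemoglobin events are 1250(1 − s) × 5.74% + 400s × 7.2% + 400(1 − s) × 11.0%.

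| s | No RBV | RBV | Events | Among RBV takers | Pooled (/1650) | Shortfall for RBV-only rows |
|---|---|---|---|---|---|---|
| 25% | 312.5 | 1337.5 | 94.0 | 7.0% | 5.7% | 18.9% |
| 50% | 625 | 1025 | 72.3 | 7.05% | 4.4% | 37.9% |
| 75% | 937.5 | 712.5 | 50.5 | 7.1% | 3.1% | 56.8% |

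The rate among RBV takers hardly moves, while the pooled rate nearly halves.

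As a rough guide only, the two earlier non-cirrhotic studies M11-646 and M13-098 had GT1b shares of 32.3% and 41.4%. Those shares would leave about 404 and 518 subjects without RBV, so shortfalls of 404 / 1650 = 24.5% and 518 / 1650 = 31.4%.

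**Step 5: bilirubin.** The non-cirrhotic RBV rate is (765 × 2.6% + 401 × 5.7%) / 1166 = 3.67%. Under the same mixes:
- s = 25%: (1.25 + 34.4 + 13.5 + 15.6) / 1650 = 3.9%
- s = 50%: (2.5 + 22.9 + 27.0 + 10.4) / 1650 = 3.8%
- s = 75%: (3.75 + 11.5 + 40.5 + 5.2) / 1650 = 3.7%

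The terms are, in order, no RBV, RBV non-cirrhotic, cirrhotic 12 weeks and cirrhotic 24 weeks. Here the pooled rate is stable, but it hides group rates from 0.4% to 13.5%.

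**The case against.** The best defence is that this is a single-arm study with no safety objective, that SAP 10.1 justifies one ITT-I column as the labelled treatment, and that RBV is assigned by subtype and cirrhosis, so columns with and without RBV would be confounded. The randomised comparisons were made in earlier studies. The protocol also allows further adverse-event and laboratory analyses where useful. The confounding argument stands: such columns can only be descriptive. The rest does not remove the point. The labelled-treatment remark is in the efficacy section, no subject receives an average regimen, and an optional analysis is not a plan.

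Some information can be recovered. RBV compliance is summarised with its N (SAP 9.2), so RBV-only counts can be re-based approximately. Listings cover Grade 2 or worse hemoglobin and Grade 3 or worse liver tests (SAP 11.3.2). Listings do not, however, give hemoglobin, bilirubin or adverse-event rates by regimen.

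Four stronger readings are tempting but not supported:
- *The SAP expressly divides RBV rows by all subjects.* No row-level denominator is written. For Section 11 it follows from 5.1.3. In 8.0 the safety population is named for the first list, and the RBV list states none.
- *Only safety is left unsplit.* Disposition (SAP 8.0) and the additional efficacy endpoints (SAP 10.7) are also unsplit, while exposure is categorised by duration (SAP 9.1).
- *A hepatic signal in cirrhotics would be buried.* Its percentage would be diluted: about 400 is a cap on cirrhotics, so about 1250 non-cirrhotics is an approximate minimum. But hepatic decompensation and failure has its own table and listing (SAP 11.2.1.1), and decompensation and HCC are adjudicated outcomes.
- *Bilirubin rises with RBV and longer treatment.* The protocol also attributes it to ABT-450, and the 24-week cirrhotic rate (5.2%) is below the 12-week rate (13.5%). The protocol adds that adverse-event rates were in general similar with and without cirrhosis.

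**Conclusion.** The point holds as a reporting defect that should be corrected. As written, RBV-specific percentages are taken over a population that includes subjects who receive no RBV, and no RBV-recipient denominator is given. If any GT1b non-cirrhotic subjects enrol, those percentages are below the rate among recipients by exactly the non-RBV share. Pooled hemoglobin rates are diluted similarly, because the RBV-free rate in Table 3 was 0%.

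Confidence is high on direction only. The 19% to 57% shortfall, and the fall from about 7% to between 5.7% and 3.1%, rest on an assumed GT1b share, 400 cirrhotics, and earlier-study rates carrying over.

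A reader might infer that the pooled figures are wrong. They are not: each validly describes the mixed population. The error arises when one is read as the risk of taking RBV.

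**What to change.** Keep the overall column, and make two changes.

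1. In SAP 5.1.3 and Section 11, add columns by RBV received (yes/no) and by cirrhosis for the adverse-event overview, adverse events by SOC and preferred term, and the hemoglobin and liver-test grade tables. Where numbers allow, show 12 and 24 weeks separately for RBV-treated cirrhotics. A full regimen breakdown of every safety table is not needed.
2. In SAP 8.0 and 11.2, state that the denominator for RBV dose modification, RBV interruption, RBV-related adverse events and adverse events leading to RBV modification is subjects with at least one dose of RBV.

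The cost is SAP wording and extra table columns, with no new data. Some groups will be small. The SAP should say that the RBV columns are descriptive, because RBV is assigned by subtype and cirrhosis.
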